5.2.2. Placebo

Placebo will be administered as a matching single IV infusion over 60 minutes, followed by a 15 minute 0.9% NaCl flush. The complete infusion will consist of the IV infusion and the flush following the IV infusion.

5.3. Randomization and Blinding

Once an eligible subject is at the study site and prepared to receive the study drug, the subject will be assigned the treatment allocation according to the randomization sequence. The randomization sequence will be obtained by computer-generated random numbers and provided to unblinded study site staff members who will have primary responsibility for drug dispensing. Within each cohort, eligible subjects will be randomized to receive PMN310 (N = 6) or placebo (N = 2). Subjects and study personnel will be aware of the dosage level but will be blinded to

the study drug administered (PMN310 or placebo). Only unblinded study site staff members assigned to prepare study drug will know whether a subject receives PMN310 or placebo. To maintain appropriate blinding, the unblinded pharmacist will consult the randomization sequence, prepare the PMN310 or placebo, and label the prepared study drug with the subject's study identifier and the phrase "PMN310 or placebo." The unblinded pharmacy staff will then provide prepared study drug in a blinded fashion to the Investigator (or designee) for infusion.

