5.1.2. Placebo

Placebo will consist of 100 mL 0.9% NaCl.

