5.4. Unblinding for an Individual Subject

In case of an emergency, the Investigator has the sole responsibility of determining if unblinding of a subject' treatment is warranted. Blinding should only be broken in emergency situations when knowledge of the treatment assignment is required for the assurance of the safety of the subject and the medical management of the subject. The Sponsor or representative should be contacted, when possible, before breaking the blind except in emergency circumstances when the Investigator has the sole responsibility for determining the need to unblind. Upon breaking the blind, the reason must be documented, and the Sponsor should be immediately notified. The applicable standard operating procedures (SOPs) will be followed for breaking the blind.

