5.6. Storage, Handling, and Accountability of Study Drug

PMN310 will be supplied directly to the study site. The study site will acknowledge receipt of the shipment and record inventory and usage of study drug on a drug disposition form. Upon arrival at the study site, vials will be stored frozen at -25°C to -15°C (-13°F to 5°F) inside the cartons to minimize exposure to light, with the cartons oriented such that the enclosed vials are in the upright position. An unblinded study monitor will perform reconciliation of the drug product.

Used vials will be destroyed according to the site's policy for investigational drug destruction. Unused vials will be either destroyed at the study site or returned to the Sponsor, as agreed between the site and Sponsor. Before disposal/destruction of unused vials, final drug accountability and reconciliation must be performed by the unblinded study monitor. Documentation of destruction of vials of PMN310 must be available for review by the study monitor.

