10. QUALITY CONTROL AND QUALITY ASSURANCE

The following steps will be taken to ensure the accuracy, consistency, completeness, and reliability of the data:

- Training of site personnel on all protocol procedures during site initiation visits
- Routine study site monitoring
- CRF review against source documents
- Data management quality control checks

In addition, the Sponsor or designee may conduct periodic site audits.

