10.1. Study Monitoring and Site Audits

Representatives designated by the Sponsor will monitor the clinical study in accordance with current FDA, ICH, national and local regulations and guidelines. During the clinical study, Clinical Monitors will visit the study site(s) on a regular basis to assess and assure satisfactory enrollment rates, data recording, maintenance of required regulatory documentation, and protocol compliance. The Investigator must ensure that all requested materials, including subject charts, CRFs, source documents, laboratory records, and study drug inventory records are available to the Clinical Monitor. The Investigator must also ensure that he/she and other qualified personnel are available at each study site visit to discuss and resolve any study-related issues.

As stipulated by 21 CFR 312.58 and ICH guidelines for Good Clinical Practice (GCP), representatives of the Sponsor, the FDA, or other regulatory agencies may conduct periodic study site audits. These representatives must have access to all requested materials, including subject charts, CRFs, source documents, laboratory records, and study drug inventory records.

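### Do the monitors' rights to drug records undercut the statement that only the drug preparers know the arm?

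*Protocol*

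**What the plan says.** Protocol 5.3 describes a pharmacist-level blind. Subjects and study personnel know the dose level but not whether the infusion is active. It then closes the list of people who do know: "Only unblinded study site staff members assigned to prepare study drug will know whether a subject receives PMN310 or placebo". SAP 5.7.1 repeats the sentence. Protocol 5.4 covers the exception: "Blinding should only be broken in emergency situations when knowledge of the treatment assignment is required".

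Protocol 5.6 deals with drug accountability. The site must "record inventory and usage of study drug on a drug disposition form", and "An unblinded study monitor will perform reconciliation of the drug product". The section says a second time that final accountability, before unused vials are disposed of, belongs to the unblinded monitor. Its last sentence lets the study monitor review vial destruction records, this time without the word unblinded.

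Protocol 10.1 is the general monitoring section. It says that "Representatives designated by the Sponsor will monitor the clinical study". Among the materials that may be requested, it has the Investigator ensure that "subject charts, CRFs, source documents, laboratory records, and study drug inventory records are available to the Clinical Monitor". A second paragraph gives Sponsor, FDA and other regulatory representatives the same access for audits. Section 10 also lists "CRF review against source documents" among the quality steps.

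**The concern.** Taken literally, the sections disagree about who may hold information that reveals the arm. A monitor designated by the Sponsor is not a site employee who prepares drug, so the unblinded monitor of 5.6 falls outside the closed list in 5.3. Section 10.1 seems to go further. It names one role, gives no blinding status, and lists drug records beside CRFs.

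The records could matter. Protocol 5.1.2 states: "Placebo will consist of 100 mL 0.9% NaCl". PMN310 comes in vials, so a record showing no vials used for a subject identifies placebo.

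The stake would be the adverse event data, which are part of the primary endpoint (protocol 2.2.1). The Investigator grades severity (7.1.15.2) and causality (7.1.15.3) and sits on the Safety Review Committee (3.1.2). AE grades can also pause escalation (5.5). Section 10.1 makes this same person responsible for having the drug records available.

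**Working it through.** The plan states no figure on this point, so the check is a comparison of sections.

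**1. Protocol 5.3 and SAP 5.7.1 against protocol 5.6.** The mismatch is real and needs no inference: 5.3 omits a role that 5.6 names twice. But 5.6 calls that role unblinded in plain terms. The omission does not lead anyone meant to be blinded to believe they may see the arm. The closed list is incomplete; the separation of duties is not missing.

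**2. Protocol 5.6 against 10.1.** Three features of 10.1 matter.
- The duty covers materials that are requested. A blinded monitor who checks CRFs and leaves drug records to the monitor of 5.6 breaches neither section.
- The text speaks of Clinical Monitors in the plural before referring to the Clinical Monitor, and never says that this person is blinded.
- It names inventory records. Section 5.6 separates inventory from usage, and it is usage by subject that would show the arm.

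So 5.3, 5.6 and 10.1 can be followed together, apart from the omission in step 1.

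**3. Would the record show the arm?** That depends on the layout of the drug disposition form, which is not given. With 8 subjects per cohort and 4 or 5 cohorts (protocol 9.2):
- stock totals only: 0 subjects identified;
- usage by dosing date, if the two sentinels of a cohort are dosed on different days (not stated): at least 2 × 4 = 8 or 2 × 5 = 10;
- usage by subject: 8 × 4 = 32 or 8 × 5 = 40.

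A range from nobody to the whole study reflects an unknown form. It does not estimate an effect.

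**4. Would it reach the endpoint?** The monitor rates no adverse event; the Investigator does. Ensuring that a record is available does not require seeing it. Section 5.3 puts the randomization sequence and preparation with unblinded staff, and 5.2.1 leaves preparation details to a Pharmacy Manual. Safety results are summarised descriptively (SAP 8), and SAP 6.6 plans no formal hypothesis testing. No test, interval or sample size depends on the wording.

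**5. What would new wording gain?** Confining inventory records to the unblinded monitor alone would conflict with the audit and inspection access in the second paragraph of 10.1. A complete list of unblinded people would also have to cover whoever generates and supplies the randomization sequence (5.3) and anyone told the arm in an emergency (5.4). Careful wording could do this, but it would record a separation that 5.6 already sets up.

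**The case for a change.** The strongest case for a change is that the text should be true as written and costs little to correct. The word *only* in 5.3 is contradicted by 5.6. The missing qualifier occurs twice, in 10.1 and in the last sentence of 5.6. SAP 3.1 cites three protocol clarification letters, yet SAP 5.7.1 still repeats the 5.3 sentence, so the SAP itself carries no correction. The person whose blind most needs protection is the Investigator, and 10.1 places a duty about drug records on that person. A few sentences would settle it, with no new staff.

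The inconsistency stands, and a study report that describes the blind should name the unblinded monitor of 5.6. The step from there to a weakness in the trial does not stand. It needs four things the documents do not say: that the usage record is kept so as to link to subjects, that the inventory records of 10.1 include it, that a blinded monitor would ask for it, and that it would pass before the Investigator's eyes. The specific section on accountability points the other way on who handles drug records. The documents do not show that anyone is unblinded by this route.

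**Conclusion.** No change to the plan is called for. Protocol 5.3 and SAP 5.7.1 leave out one unblinded role, and 10.1 and the last sentence of 5.6 omit a qualifier. These are clerical slips. The safeguard itself, drug accountability by an unblinded monitor, is already in 5.6, and staff working under the protocol would apply it. No effect on adverse event ratings can be derived from the documents, and no analysis or conclusion would differ with tidier wording.

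This rests on three assumptions: that monitoring follows the specific rule in 5.6 rather than the broadest reading of 10.1; that unblinded pharmacy staff hold the drug records, as 5.3 and 5.2.1 imply; and that nothing in the Pharmacy Manual or the clarification letters, which were not supplied, says otherwise. If a monitor who reviews CRFs were found reading usage by subject while meant to be blinded, that would be a departure from 5.3 in conduct, to be reported as a deviation. It would not show that the planned analysis was wrong.

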5.4. Unblinding for an Individual Subject

In case of an emergency, the Investigator has the sole responsibility of determining if unblinding of a subject' treatment is warranted. Blinding should only be broken in emergency situations when knowledge of the treatment assignment is required for the assurance of the safety of the subject and the medical management of the subject. The Sponsor or representative should be contacted, when possible, before breaking the blind except in emergency circumstances when the Investigator has the sole responsibility for determining the need to unblind. Upon breaking the blind, the reason must be documented, and the Sponsor should be immediately notified. The applicable standard operating procedures (SOPs) will be followed for breaking the blind.

5.5. Dose Escalation/Stopping Rules

Dose escalation will be paused for review if any of the following occur, Two or more of the subjects in a cohort develop Grade ≥ 2 AEs in the same category.

- One or more subjects in a cohort develop Grade ≥ 3 AEs.
- It is determined that the limit of safety and/or tolerability has been reached as determined by the SRC.

The Sponsor or SRC may pause and then stop dosing within a cohort or decide to not dose escalate to a higher dose if it is determined that any AE is occurring that is intolerable or poses a medically unacceptable safety risk.

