Each dose cohort will consist of 8 subjects (6:2; PMN310:placebo). To evaluate the short term safety and tolerability of PMN310, each cohort will enroll a sentinel group of 2 subjects (1:1, PMN310:placebo) who will be dosed prior to dosing the remaining 6 subjects in the cohort (5:1, PMN310:placebo). The Safety Review Committee (SRC) will review all safety data collected through 48 hours postdose from the 2 sentinel subjects to determine the acceptability of proceeding with dosing of the remaining 6 subjects in the cohort.

Dose escalation to the next cohort will only occur after approval by the SRC. The SRC will determine the acceptability of proceeding with enrollment of the next cohort based on review of safety and any available PK data at the time of review through 7 days postdose for a minimum of 6 of 8 subjects per cohort.

In the event that important safety concerns are observed at any time during the study, administration of study drug will be paused, subjects in the subsequent cohort(s) will not receive further study drug until further review of the safety data has occurred, and subsequent recommendations and approval have been provided by the SRC.

Study Population:

Inclusion Criteria:

Subjects must meet all of the following inclusion criteria to be eligible for this study:

- 1. Male and females, 18 to 65 years of age, inclusive, at time of Screening.
 - a. Female subjects of childbearing potential must not be breastfeeding and must have no plans to become pregnant during the course of the study through 120 days after infusion of study drug. Female subjects of childbearing potential who are heterosexual must agree to use 1 of the following methods of contraception considered to be highly effective (i.e., results in < 1% failure rate when used consistently and correctly) from Screening through 120 days after the last dose of study drug:

- Intrauterine device or intrauterine system in place for at least 3 months prior to first dose.
- Partner has had a vasectomy ≥ 4 months prior to participation. Vasectomy in the partner is considered to be highly effective only if the partner is the sole sexual partner of the female subject of child-bearing potential and the vasectomy (as communicated to the subject by the vasectomized partner) was medically assessed as surgically successful.

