3.1.1. Dose Escalation Rules

[figure not shown]
Each dose cohort will consist of 8 subjects (6:2; PMN310:placebo). To evaluate the short term safety and tolerability of PMN310, each cohort will enroll a sentinel group of 2 subjects (1:1, PMN310:placebo) who will be dosed prior to dosing the remaining 6 subjects in the cohort (5:1, PMN310:placebo). The first two sentinel subjects for Cohort 1 (age < 50) will have MRIs performed and read locally. The SRC will review all safety data collected through 48 hours postdose from the 2 sentinel subjects to determine the acceptability of proceeding with dosing of the remaining 6 subjects in the cohort. Additional details on the SRC are provided in Section 3.1.2.

Dose escalation to the next cohort will only occur after approval by the SRC. The SRC will determine the acceptability of proceeding with enrollment of the next cohort based on review of safety and any available PK data at the time of review through 7 days postdose for a minimum of 6 of 8 subjects per cohort. Doses to be evaluated are presented in Section 5.2.1.

In the event that important safety concerns are observed at any time during the study, administration of study drug will be paused, subjects in the subsequent cohort(s) will not receive further study drug until further review of the safety data has occurred, and subsequent recommendations and approval have been provided by the SRC. Dose escalation/stopping rules are detailed in Section 5.5.

A schematic illustrating the study design is provided in Figure 1.

Figure 1: PMN310-101 Study Schema Per Cohort

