3.1.2. Safety Review Committee

The SRC will be responsible for the review of safety and any available PK data at the time of review, and making determinations regarding the acceptability of proceeding with dosing of the remaining 6 subjects in a cohort (based on review of sentinel subjects) and dose escalation to the next cohort. The SRC will be comprised of the Study Investigator, Medical Monitor, and Sponsor Medical Director. At a minimum, the SRC will review safety data assessments collected 48 hours after the sentinel subjects have been dosed in each cohort and ≥ 7 days post-dose for a minimum of 6 of 8 subjects per cohort prior to each dose escalation. The SRC charter will specify operational details pertaining to roles and responsibilities, data to be reviewed, review frequency, and reporting.

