7.1.15.2. Assessment of Adverse Event Severity

The Investigator will assess the intensity of each AE and SAE reported during the study on the basis of his or her clinical judgement.

The classifications in Table 1 should be used in assigning intensity of each AE recorded in the CRF.

Table 1: Classification of Adverse Events by Intensity

Intensity (Grade)	Definition						
Mild AE (Grade 1)	An event that is easily tolerated by the subject, causing minimal discomfort and not interfering with everyday activities.						
Moderate AE (Grade 2)	Some interference with activity not requiring medical intervention						
Severe AE (Grade 3)	 Prevents daily activity and requires medical intervention An event that, at the time of occurrence, put the subject at risk of death or resulted 						
	in a persistent or significant disability or incapacity.An event that resulted in death						

AE = adverse event

Any AE that changes in intensity or grade during a single occurrence of an AE will be recorded in the CRF at the highest level experienced by the subject.

An AE that is assessed as severe should not be confused with an SAE. Severity is a category used for rating the intensity of an AE (such as mild, moderate, or severe myocardial infarction). An AE, however, may be of relatively minor medical significance (e.g., a severe headache). Both AEs and SAEs can be assessed as severe. An AE is considered serious when it meets criteria for one of the predefined outcomes described in Section 7.1.15.1.

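### A Grade 3 or higher AE pauses dose escalation for review, but no stated rule holds the remaining infusions in the same cohort until that review

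*Protocol*

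**What the plan says.** Protocol 5.5 lists three conditions: two or more subjects in a cohort with Grade 2 or higher AEs of the same category, one or more subjects with a Grade 3 or higher AE, or an SRC finding that the limit of safety or tolerability has been reached. One mandatory consequence is attached to them: "Dose escalation will be paused for review if any of the following occur". The following paragraph deals with dosing inside a cohort and is permissive: "The Sponsor or SRC may pause and then stop dosing within a cohort", where an AE is judged intolerable or a medically unacceptable risk. SAP 5.3 repeats both paragraphs.

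The synopsis and Protocol 3.1.1 contain a stronger instruction: "In the event that important safety concerns are observed at any time during the study, administration of study drug will be paused", with SRC review and approval needed before dosing resumes. The condition, important safety concerns, has no definition by grade, count or type. In 3.1.1 the next sentence reads "Dose escalation/stopping rules are detailed in Section 5.5"; the synopsis has no such pointer, and SAP 5.3 has no such instruction.

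Two SRC reviews are fixed in advance. Before the remaining six subjects of a cohort are dosed, "The SRC will review all safety data collected through 48 hours postdose from the 2 sentinel subjects" (3.1.1). Section 3.1.2 confirms it: "At a minimum, the SRC will review safety data assessments collected 48 hours after the sentinel subjects have been dosed in each cohort". It adds a review of at least 7 days of data in at least 6 of 8 subjects before escalation. Other arrangements go to the charter: "The SRC charter will specify operational details pertaining to roles and responsibilities, data to be reviewed, review frequency, and reporting".

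Table 1 in 7.1.15.2 describes Grade 3 as "Prevents daily activity and requires medical intervention"; the table goes on to risk of death and death.

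**The concern.** This is a first-in-human study, and the AE counts in 5.5 are the only objective pause triggers in the protocol and SAP. The section is titled as stopping rules, yet the action tied to its most serious trigger concerns the next dose level. Subjects still waiting for the same dose that was followed by a severe event are not mentioned in that action.

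If one of the six non-sentinel subjects has a Grade 3 event after infusion, a site following 5.5 literally must stop escalation and await a review. It is not told to withhold the next infusion in the same cohort meanwhile, and 5.5 sets no time limit for the review. Whether that infusion goes ahead then depends on someone deciding, after the event, that it counts as an important safety concern or that the discretionary pause should be used. The protocol allows up to 2 sites and up to 2 more if enrollment is difficult, so that decision may not always fall to the same person.

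**Working it through.** **1. Which provision holds which infusions**

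| Provision | What sets it off | What it requires | Undosed subjects in the same cohort held? |
|---|---|---|---|
| Protocol 5.5, first part; SAP 5.3 | Grade 3 or higher AE in one subject (among others) | Escalation pause, for review | Not stated |
| Protocol 5.5, second part; SAP 5.3 | Judgement that an AE is intolerable or an unacceptable risk | Nothing; a within-cohort pause is allowed | Only if chosen |
| Protocol 3.1.1; synopsis | Important safety concerns (undefined) | Study drug pause until SRC approval | Wording is wide enough, but only if the event is judged to qualify |
| Protocol 3.1.1 and 3.1.2, sentinel review | Always | SRC review of 48-hour sentinel data | Yes, the remaining 6, until that review |
| Protocol 3.1.2, pre-escalation review | Always | SRC review of at least 7 days of data in at least 6 of 8 | No |

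Because 5.5 treats escalation and within-cohort dosing in separate paragraphs, one mandatory and one permissive, the escalation pause cannot simply be read as a dosing hold. The cross-reference in 3.1.1 joins the sections, but it does not say that a 5.5 trigger is an important safety concern.

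SAE reporting does not close the window either. Section 7.1.15.2 warns against confusing a severe AE with an SAE, and 7.1.15.8 sends SAE reports to pharmacovigilance within 24 hours without mentioning a dosing hold.

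**2. How many infusions fall in the window**

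Inputs from Protocol 3.1.1 and 9.2: 8 subjects per cohort, made up of 2 sentinels (1 PMN310, 1 placebo) and 6 others (5 PMN310, 1 placebo). Check: 1 + 5 = 6 on PMN310 and 1 + 1 = 2 on placebo; 5 cohorts x 8 = 40, the planned total.

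- Sentinel event within 48 hours: the other 6 already wait for SRC review, so there is no gap.
- Sentinel event after the 48-hour review: at most 8 - 2 = 6 undosed, 5 of them on PMN310.
- Event in the first non-sentinel: at most 6 - 1 = 5 undosed. If that subject received PMN310, 5 - 1 = 4 of them are on PMN310; if placebo, all 5.

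The counts fall as dosing proceeds, and are zero once all 8 are dosed.

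**3. How often an automatic hold could be set off**

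The documents give no AE rates. Let p be an assumed per-subject probability of a Grade 3 or higher AE from any cause, independent between subjects and equal in both arms. The probability that a cohort of 8 meets the trigger is 1 - (1 - p)^8. The probability of an event in at least one of the first 5 of the 6 non-sentinels, so that someone may still be undosed, is 1 - (1 - p)^5; this leaves out late sentinel events.

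| Assumed p | At least 1 of 8 | At least 1 of first 5 non-sentinels |
|---|---|---|
| 1% | 1 - 0.99^8 = 0.077 | 1 - 0.99^5 = 0.049 |
| 2% | 1 - 0.98^8 = 0.149 | 1 - 0.98^5 = 0.096 |
| 5% | 1 - 0.95^8 = 0.337 | 1 - 0.95^5 = 0.226 |

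The last column assumes one-at-a-time dosing with the event known before the next infusion. If several subjects are dosed together, or the event appears late, fewer infusions remain to hold.

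**The case against.** The best defence is that the protocol, read as a whole, already covers this. Section 3.1.1 makes a study drug pause mandatory at any time in the study, its next sentence points to 5.5, and an ordinary reader would take a Grade 3 event as an obvious example of an important safety concern. Section 5.5 also adds an event-driven review beyond the two fixed ones and gives the Sponsor and SRC authority to stop dosing within a cohort. Much of this stands. The trigger does have a consequence, the residual exposure is limited to infusions given between the event and the review, and most SRCs would probably pause. What the defence cannot supply is a sentence saying that those infusions wait.

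A second argument is that the triggers are all-cause: they count placebo subjects, and 7.1.15 has procedure complications recorded as AEs, with a lumbar puncture on Day 3 in every cohort. Leaving holds to a committee that includes the Investigator and Medical Monitor avoids needless delay. That is a fair reason to let the SRC release a hold quickly. It is weaker as a reason for infusing the next subject before the SRC has looked.

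Third, the SRC charter, the three clarification letters listed in SAP 3.1, and Figure 1 (the per-cohort schema) were not available. Any of them might contain a hold or a dosing interval. This stands as a limit on the point.

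**Conclusion.** The point holds as a gap in the stated rule. A Grade 3 or higher AE pauses escalation and prompts a review, but nothing in the available protocol or SAP text makes undosed subjects in the same cohort wait for it. At most 5 infusions are exposed after an event in the first non-sentinel, and at most 6 after a late sentinel event. Both maxima rest on the 2 + 6 cohort split; actual numbers depend on dosing spacing.

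A reader might infer more, in three ways that the documents do not support:

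- That the study has no mandatory pause of dosing, or that a Grade 3 event goes unreviewed. Sections 3.1.1 and 5.5 say otherwise; the weakness is that the first rests on an undefined term and the second stops short of the current cohort.
- That the next, higher-dose cohort is similarly exposed. An escalation pause most naturally covers infusions at the higher dose, and 3.1.1 names subsequent cohorts as not to be dosed during its pause.
- That the Grade 2 same-category trigger needs the same automatic hold. That is a trade-off, because lumbar puncture complications could set it off often, and the documents give no rates with which to weigh it.

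This should be changed because it concerns subject safety and is cheap to correct. Confidence is medium, given the unseen documents and the likelihood that practice is safer than the text.

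**What to change.** In Protocol 5.5, state that a Grade 3 or higher AE in any subject pauses both dose escalation and further dosing of undosed subjects in that cohort until the SRC has reviewed the event and released the hold. In 3.1.1 and the synopsis, state that important safety concerns include this trigger. Let the SRC release the hold promptly where the cause is clearly something other than study drug, such as a lumbar puncture complication. If the charter or a clarification letter already contains the hold, cite it in 5.5.

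The cost is a few sentences in a protocol amendment. The sample size, randomization and analyses do not change, and aligning SAP 5.3 is optional. In conduct, the price is an occasional short delay for events unrelated to drug, including events on placebo. At the assumed rates of 1%, 2% and 5%, about 8%, 15% and 34% of cohorts would meet the trigger. Fewer would have infusions actually held, because an event after the last subject is dosed holds nobody in that cohort, and escalation is already paused under the present rule.
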